4.1 Overall Design

This is a Phase IV, local, single center, open label, pilot, randomized controlled clinical study to compare the efficacy and safety of Crinone® versus combination medication. The study population are infertile women who receive FET in ACs. This study plans on including 334 participants from a single reproductive center over 25 months. Participants that enter the study will be randomized into either of the two groups. The study intervention drug received by the participant is determined based on the result of randomization. The randomization procedure is described in [Section 6.3](#). The overall scheme of the study is in [Section 1.2](#) and the Schedule of Activities at each visit can be found in [Section 1.3](#).

The participants will sign an ICF; the participants are free to withdraw at any time without prejudice to their medical care, and they are not obliged to state their reasons for withdrawal. Upon site initiation, the Investigator site will enroll the eligible participants who meet the inclusion and none of the exclusion criteria in a consecutive manner until the enrollment target is reached. The study will consist of a screening period, followed closely by procedures from endometrial transformation to ongoing pregnancy assessment, which lasts for approximately 75 days. Study treatment will start from the day of endometrial transformation (Day -5) until ongoing pregnancy assessment, which occurs between 10-12 weeks of pregnancy (8-10 weeks after ET). The middle number of 9 weeks (Day 63) after ET is used to define the study day with a window of 10 days on each side as leeway. The treatment will be administered for approximately 75 days.

Relevant data according to study requirements will be recorded in standard CRF. When the study starts, this reproductive center will include participants who enter the cycle. The information of the qualified yet excluded participants who have signed ICFs will be recorded, and the reason for their exclusion will also be recorded in the CRF. If a participant has entered the study and later discontinue their study intervention, the reason for discontinuing the study intervention will be recorded in the CRF.

[figure not shown]
Participant follow-up will occur until her ongoing pregnancy is confirmed and/or until End of Study (defined in [Section 4.4](#)).

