5.1 Inclusion Criteria

Participants are eligible to be included in the study only if all the following criteria apply:

1. Are 20 through 38 years old women who will receive artificial FET cycle study interventions
2. No more than two Day 5 embryos are planned to be transferred (follow the clinical practice of the study site)
3. Have received estradiol valerate for no more than 20 days
4. Have a transitional-endometrium of ≥ 8 mm
5. Have normal uterine cavity
6. Can give signed informed consent, as indicated in [Appendix 2](#) (Study Governance), which includes compliance with the requirements and restrictions listed in the ICF and this protocol.
7. Are willing to follow the study protocol and able to complete the study

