6.3 Measures to Minimize Bias: Study Intervention Assignment and Blinding

6.3.1 Study Intervention Assignment

Participants will be randomized in a 1:1 ratio to receive either Crinone® or the combination medication group on the day of ET.

The trial is designed as a single center trial, and randomization will be conducted on the ET day by using the block permutation method and stratified by age group (ages 20 to 35 years, or ages 35 years and over), which will guarantee that a balanced number of participants will be obtained between Crinone® and the combination medication groups inside each age stratum. If an error occurs (for example if the wrong list is used), the participant should continue with their assigned study intervention, and the next participant should still be assigned the next available number and study intervention of the correct list. The site must not attempt to “correct” for the error (i.e., if a participant is on the Crinone® list instead of the

combination medication group list, the site must not try to assign the Crinone® participant to the combination medication group list to offset this). Since ACCESS is an open-labeled observational study, baseline characteristic analysis will be presented to show whether the participants were well-stratified by age between the two study intervention groups.

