- Study intervention A (Crinone® group): Randomized participants will be given Progesterone gel 8% (Crinone®) 90 mg/p.v./q.d from the day of endometrial transformation. It will be suggested that they administer the drug in the morning and at the same time of day throughout the trial. A β -hCG test will be done 14 days after ET. If serum β -hCG levels are negative, the study will be discontinued. If the result of the β -hCG test is positive, Crinone® administration will continue with the above regimen. At 35 days after ET, an ultrasound will be done to detect the number of gestational sacs to confirm the results of clinical pregnancy. If clinical pregnancy is positive, continue Crinone® administration until ongoing pregnancy assessment. Should a miscarriage occur at any point, Crinone® administration will be discontinued.
- Study intervention B (Crinone® + Duphaston® group): Randomized participants will be given Progesterone gel 8% (Crinone®) 90 mg/p.v./q.d from the day of endometrial transformation, following which Duphaston® at 10 mg/p.o./bid will be administered from the day of ET. It will be suggested that they administer the drugs in the morning and at the same time of day throughout the trial. A β -hCG test will be done 14 days after ET. If serum β -hCG levels are negative, the study will be discontinued. If the result of the β -hCG test is positive, the combination medication will continue with the above regimen. At 35 days after ET, an ultrasound will be done to detect the number of gestational sacs to confirm the results of clinical pregnancy. If clinical pregnancy is positive, continue combination medication until ongoing pregnancy assessment. Should a miscarriage occur at any point, combination medication will be discontinued.

All participants will receive oral estradiol valerate continuously and the dose of estradiol valerate will be adjusted according to local practices.

The following data will be collected:

- Duration and total dosage of estradiol valerate

- Date of ET
- Number of embryo(s) transferred (no more than 2)
- Embryo quality
- Check I/E criteria
- Recording of AEs
- Concomitant medications prescribed and reasons.

Visit 4 (β -hCG positive assessment)

Participants treated by ART are routinely monitored for early detection of pregnancy by measuring serum β -hCG concentration according to the site's routine clinical practices.

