**14 Efficacy Analyses**

**14.1 Primary Endpoint: Ongoing Pregnancy**

#### 14.1.1 Primary Objective: Analysis of the primary endpoint Ongoing Pregnancy

Analysis (Analysis Population)	Derivation	Statistical Analysis Methods	Missing data handling
Primary endpoint: Ongoing pregnancy assessment at 10-12 weeks of pregnancy [8-10 weeks after ET]			
Primary (ITT)	Ongoing pregnancy rate (%): =100 * number of subjects with ongoing pregnancy/number of subjects with ET cycle.	

Point estimate and 95%CI for each study intervention groups (Clopper-Pearson)

Point estimate and 90%CI for difference between two study intervention groups (stratified Miettinen & Nurminen (MN) method (see Miettinen & Nurminen, 1985))

It will be computed with the SAS® 9.4 FREQ procedure, using the riskdiff (COMMON) option in the Table statement and specified alpha=0.1. The results could be found in the ODS CommonPdiff table (method=' Summary Score')

	Missing=Failure
Supportive (PP)	

Time window: from the start date of first ET to the end of study.

Numerator: The subjects with ongoing pregnancy will be determined to be those with positive ongoing pregnancy result in the "Ongoing Pregnancy Assessment" eCRF page

Denominator: The subjects with ET cycle will be determined as those with ET date in "Embryo Transfer" eCRF page.

		

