#### 14.2 Secondary endpoint

Analysis (Analysis Population)	Derivation	Statistical Analysis Methods	Missing data handling
Secondary Endpoint: <math>\beta</math>-hCG positive			
Secondary (ITT)	$\beta$ -hCG positive rate (%): =100 * number of subjects with positive $\beta$ -hCG /number of subjects with ET cycle.	Same as method in the section 14.1.1	Next observation carried backward (NOCB). Missing assessment outcomes prior to positive pregnancy assessment outcome will be imputed to be positive. Note: imputation is only valid for those subjects with following positive assessment outcomes and carried backward. Otherwise, missing=failure.
Supportive (PP)	
 
Time window: from the start date of first ET to the end of study.
 
Numerator: The subjects with positive <math>\beta</math>-hCG will be determined to be those with positive <math>\beta</math>-hCG result in the "<math>\beta</math>-hCG Level" eCRF page at <math>\beta</math>-hCG positive assessment visit.
 
Denominator: The subjects with ET cycle will be determined as those with ET date in "Embryo Transfer" eCRF page.
 
		
Secondary Endpoint: Implantation			
Secondary (ITT)	Implantation rate (%): =100 * number of gestational sacs observed / number of embryos transferred.	Same as method in the section 14.1.1	Same as above
Supportive (PP)	
 
Time window: from the start date of first ET to the end of study.
 
Numerator: The number of gestational sacs will be obtained in the "Clinical Pregnancy Assessment" eCRF page.
 
Denominator: The number of embryos transferred will be obtained in the "Embryo Transfer" eCRF page.
 
		
Secondary Endpoint: Clinical pregnancy			
Secondary (ITT)	$\beta$ -hCG positive rate (%): =100 * number of subjects with clinical pregnancy/number of subjects with ET cycle.	Same as method in the section 14.1.1	Same as above
Supportive (PP)	
 
Time window: from the start date of first ET to the end of study.
 
		

	
 
Numerator: The subjects with clinical pregnancy will be determined to be those with positive clinical pregnancy result in the "Clinical Pregnancy Assessment" eCRF page
 
Denominator: The subjects with ET cycle will be determined as those with ET date in "Embryo Transfer" eCRF page.
 
		

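### Implantation is a per-embryo rate given one-outcome-per-woman intervals; with double transfers and positive within-woman correlation, the 90% interval for the difference is somewhat too narrow (minor).

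*SAP*

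**What the plan says.** SAP 14.2 gives the endpoint as "Implantation rate (%): =100 * number of gestational sacs observed / number of embryos transferred". Both counts are pooled over women, with the denominator taken from the embryo transfer page of the eCRF. The method entry in the same row reads "Same as method in the section 14.1.1".

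SAP 14.1.1 sets out that method for ongoing pregnancy, where numerator and denominator both count women. It has two parts: a 95% Clopper-Pearson interval for each arm, and "Point estimate and 90%CI for difference between two study intervention groups", computed by the Miettinen-Nurminen method stratified by age group. Protocol 9.4.3 says only that secondary endpoints are handled in a manner similar to the primary.

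On the units involved:
- Protocol 6.3.1: "Participants will be randomized in a 1:1 ratio". The unit randomised is the woman.
- Protocol 5.1: "No more than two Day 5 embryos are planned to be transferred", following site practice. Appendix 4 (Visit 3) records the number transferred, with the same limit of two.
- SAP 8.2 and 14.1.2 define one-embryo and two-embryo subgroups and compare the share of single transfers between arms, so a mix is foreseen.

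Neither document mentions clustering, a robust variance or a woman-level form of implantation.

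**The concern.** Clopper-Pearson and Miettinen-Nurminen treat each unit in the denominator as an independent yes/no outcome. That suits the endpoints counted per woman. Implantation is the only endpoint sent to 14.1.1 whose denominator counts embryos. Two embryos in the same woman share her endometrium, age and treatment, so positively correlated outcomes are the natural worry, although the documents give no figure. With such correlation, the pooled embryo count overstates the information and the interval is too short.

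At stake is the nominal level of an interval on a named secondary efficacy endpoint. Protocol 9.1 and SAP 9 rule out formal testing, so intervals are the study's only inferential output, and SAP 4 says the planned analyses will also appear in manuscripts.

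**Working it through.** **Inputs from the documents.** "This study plans on including 334 participants from a single reproductive center over 25 months" (Protocol 4.1), allocated 1:1, gives 334/2 = 167 women per arm. There are two age strata (Protocol 6.3.1) and one or two embryos per woman. The plan states no figure for implantation that could be reproduced.

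**Assumed, because the documents are silent.** Implantation rate p = 40% per embryo (the 40% in Protocol 2.2 is a clinical pregnancy rate per cycle, not an implantation rate); 25% of women in the older stratum (125/42 per arm); no true difference; f and rho as shown.

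**Formula.** With n women per arm, the variance of total sacs is n·p(1−p)·[1 + f + 2f·rho]. The binomial method assumes n·p(1−p)·[1 + f]. The ratio is the design effect, 1 + 2f·rho/(1 + f), and the standard error is understated by its square root, which never exceeds sqrt(1 + rho) for positive rho. Approximate coverage of a nominal 90% interval is 2Φ(1.645/factor) − 1.

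- f 25%, rho 0.1: 1 + 0.05/1.25 = 1.040; factor 1.020; coverage 89.3%
- f 50%, rho 0.2: 1 + 0.20/1.50 = 1.133; factor 1.065; coverage 87.8%
- f 100%, rho 0.3: 1 + 0.60/2 = 1.300; factor 1.140; coverage 85.1%
- f 100%, rho 0.6: 1 + 1.20/2 = 1.600; factor 1.265; coverage 80.7%

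**Simulation.** 20,000 trials per setting. The planned interval is an age-stratified Miettinen-Nurminen score interval on embryo counts. The comparator is a ratio-estimator interval clustered on the woman. Half-widths are in percentage points.

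| f, rho | Planned 90% CI: coverage | Half-width, planned / clustered | Ratio | Per-arm Clopper-Pearson 95%: coverage |
|---|---|---|---|---|
| 25%, 0.1 | 89.7% | 7.87 / 8.05 | 1.023 | 95.8% |
| 50%, 0.2 | 87.9% | 7.18 / 7.66 | 1.067 | 94.3% |
| 100%, 0.3 | 84.5% | 6.22 / 7.11 | 1.143 | 92.3% |
| 100%, 0.6 | 80.0% | 6.21 / 7.88 | 1.269 | 88.4% |

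Clustered intervals for the difference covered 89.5% to 90.3% in all settings.

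**Sensitivity.**
- The exact SAS summary-score weights were not reproduced in this run. An inverse-variance combination of the stratum score intervals and an unstratified score interval agree with the table to within 0.1 point.
- Varying p from 0.30 to 0.60, the older stratum from 10% to 40%, and adding a 10-point true difference with an age gradient gives 88.4–89.7%, 87.6–88.1%, 84.5–85.3% and 80.0–81.2% in the four cases.
- A separate run (10,000 trials, strata 120/47) at f 50% gave 88.7% (rho 0.1), 86.5% (rho 0.3) and 84.4% (rho 0.5), so a mixed population with stronger correlation also loses several points.
- With rho 0 or all single transfers, coverage is 89.8% to 90.3%. With rho −0.1 it is 90.7%, 91.4%, 91.7% and 91.3% at f 25%, 50%, 75% and 100%, so the interval is slightly too wide.

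**The case against.** The size rests wholly on assumption. Neither f, rho nor an implantation rate appears in the documents, and the number transferred follows site practice. In the mildest case the loss is 0.3 points of coverage. The 85% and 80% figures need every woman to receive two embryos, whereas the SAP plans for a mix. No hypothesis is tested and no decision uses this interval. SAP 11.3 already tabulates the number of embryos transferred by arm, so a reader who assumes a rho can work out the factor. All of this stands, and it is why the point is minor. It does not remove the mismatch: the SAP names a method for this endpoint that takes no account of the unit randomised.

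A reader might infer more than the documents support:
- That the implantation comparison is invalid or its estimates biased. The per-arm estimates are unaffected; the fault is in the interval width.
- That every interval for implantation is too narrow. The direction depends on rho, and the Clopper-Pearson interval per arm is conservative enough to stay near 95% unless f and rho are both sizeable.
- That coverage of 80% to 85% is to be expected. Those cases set f at its limit.
- That the primary endpoint shares the problem. It counts women, so it does not.

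It is also fair to object that a remedy can overreach. A plain clustered Wald interval per arm would be about 3% narrower than Clopper-Pearson with a single double transfer or with rho 0, and about 6% narrower at f 50%, rho −0.1. It would replace an interval that has no coverage deficit there. The fix below avoids that.

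**Conclusion.** The point holds, conditionally and at minor weight. If some women receive two embryos and outcomes within a woman are positively correlated, the planned 90% interval for the difference in implantation is too narrow by sqrt(1 + 2f·rho/(1 + f)). Under assumed mixed transfers (f 25% to 50%, rho 0.1 to 0.2), coverage is about 88% to 90%; about 85% and 80% are the cases with f at 100% and rho 0.3 and 0.6. The per-arm interval falls clearly short only when f and rho are both large. With all single transfers or rho 0 there is nothing to correct. These sizes assume 167 women per arm and a 40% rate, and changed little over the ranges tried. The existence of the mismatch needs no assumption, since it can be read from SAP 14.2 beside 14.1.1.

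**What to change.** In SAP 14.2, for implantation only:

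- **All transfers single:** keep 14.1.1.
- **Any woman with two embryos, difference:** within each arm and age stratum take r = total sacs / total embryos and v = [n/(n − 1)] × Σ(sacs − r × embryos)² / (total embryos)², summed over the n women. Combine the stratum differences with weights proportional to M1·M2/(M1 + M2), where M1 and M2 are the embryos transferred in each arm of that stratum, scaled to sum to 1. The 90% interval is the weighted difference ± 1.645 × sqrt[Σ weight² × (v1 + v2)].
- **Any woman with two embryos, per arm:** keep the Clopper-Pearson form, but replace the embryo number M by M / design effect and the sac count by r times that number. The design effect is v / [r(1 − r)/M] for the whole arm, and not below 1. The interval is then never narrower than planned. In simulation under the same assumptions it covered about 95% to 97%.

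The switch depends only on embryo counts, not on outcomes, so it can be fixed in advance. The protocol's wording (a similar manner to the primary) leaves room for it, and SAP 7 already changed the interval method once to suit the stratified design.

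**Cost.** One SAP cell, a few lines of code and no new data. The difference interval becomes about 2% to 7% wider under the mixed assumptions and 14% to 27% wider in the f 100% cases; it is unchanged or slightly narrower if rho is 0 or negative. The per-arm interval becomes about 0% to 7% wider under the mixed assumptions and about 15% to 27% wider in the f 100% cases. Because the stratum weights differ from those of SAS, the stratified difference may move slightly. Against an inverse-variance weighting the mean shift was 0.1 points or less in the base case, and about 0.35 points with an assumed 12-point age gradient and a 10-point true difference.

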9.4.1.2 Secondary Endpoints

- β -hCG positive

Definition: A pregnancy diagnosed by the detection of β -hCG in serum

- Implantation:

Definition: The number of gestational sacs observed by ultrasound scan

- Clinical pregnancy

Definition: A pregnancy diagnosed by ultrasound of one or more gestational sacs or definitive clinical signs of pregnancy. It includes ectopic pregnancy. Note: Multiple gestational sacs are counted as one clinical pregnancy.

- Early abortion

Definition: The spontaneous loss of an intra-uterine pregnancy prior to 12 completed weeks of gestational age.

- Bleeding (luteal phase, vaginal)

Definition: The bleeding data will be collected in a CRF after each visit by Investigators according to original medical documents.

- Luteal phase bleeding: defined as the onset of any bleeding after ET and prior to the pregnancy test. The luteal phase bleeding rate will be assessed in each group and analysed according to the pregnancy outcomes.
- Vaginal bleeding is defined as any bleeding recorded in the CRF after a pregnancy test via serum β -hCG and is considered as an AE. The vaginal bleeding rate will be assessed and compared in both groups at each visit.

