9.4.3 Analysis of Endpoints

Endpoint	Statistical Analysis Methods
Primary	
The analysis of the primary endpoint in this pilot study is essential for further planning of formal clinical trials. The analysis for the primary endpoint will estimate the ongoing pregnancy rate and its corresponding 95% CI for each group, and difference in ongoing pregnancy rate between combination medication and Crinone® and its corresponding 90% CI. The CIs for each treatment group will be calculated with the Clopper-Pearson method. The CI for the difference between the two treatment groups will be calculated with the Pearson chi-square test
 
Ongoing pregnancy rate: the number of ongoing pregnancies expressed per 100 ET cycles (from the start date of first ET to the End of Study).
 
Since the number of embryos transferred is medically known to have an impact on the chance of achieving an ongoing pregnancy rate, the rate of participants with only 1 embryo transferred within each arm will be examined. If the data suggest a possible imbalance between the two arms, pertinent subgroup analyses of the primary endpoint in participants with only 1 embryo transferred and in participants with 2 embryos transferred may be performed. Details will be specified in the Statistical Analysis Plan.

Secondary	
The analyses of secondary endpoints will take the similar manner as primary endpoint.
 
Implantation rate: The number of gestational sacs observed divided by the number of embryos transferred (usually expressed as a percentage, %).
 
β-hCG positive rate: the number of β-hCG positive participants expressed per 100 ET cycles.
 
Clinical pregnancy rate: the number of clinical pregnancies expressed per 100 ET cycles.

Endpoint	Statistical Analysis Methods
	
Luteal phase bleeding rate : the number of the participants with luteal phase bleeding expressed per 100 embryos transferred cycles.
 
Vaginal bleeding rate: the number of the participants with vaginal bleeding expressed per 100 embryos transferred cycles.

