Secondary Endpoint: Early abortion			
Secondary (ITT)	Early abortion rate (%): =100 * number of subjects with Early abortion/number of subjects with clinical pregnancy.	Same as method in the section 14.1.1	Missing=not occurred
Supportive (PP)	
 
Time window: from the start date of first ET to the end of study.
 
Numerator: The subjects with Early abortion will be determined to be those with early miscarriage date in "early miscarriage" eCRF page.
 
Denominator: The subjects with clinical pregnancy will be determined to be those with positive clinical pregnancy result in the "Clinical Pregnancy Assessment" eCRF page.
 
		

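### The SAP early-abortion rate counts ectopic pregnancies as at risk and does not restrict its numerator to the women in its denominator (minor)

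*SAP*

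**What the plan says.** Protocol 9.4.1.2 defines early abortion as "The spontaneous loss of an intra-uterine pregnancy prior to 12 completed weeks of gestational age". In the same section it says of clinical pregnancy: "It includes ectopic pregnancy".

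Protocol 9.4.3 states that "The analyses of secondary endpoints will take the similar manner as primary endpoint". It then sets out rates for implantation, β-hCG positivity, clinical pregnancy and the two bleeding endpoints, but none for early abortion. The only formula is therefore in SAP 14.2:

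- **Rate:** "100 * number of subjects with Early abortion/number of subjects with clinical pregnancy".
- **Numerator:** "The subjects with Early abortion will be determined to be those with early miscarriage date in" the early-miscarriage eCRF page.
- **Denominator:** subjects with a positive result on the clinical pregnancy eCRF page, with no intra-uterine condition.
- **Window:** "from the start date of first ET to the end of study".
- **Missing outcome:** "Missing=not occurred". For ongoing pregnancy, SAP 14.1.1 uses "Missing=Failure".
- **Method:** as for the primary endpoint, that is, a Clopper-Pearson interval per arm and a stratified Miettinen-Nurminen 90% interval for the difference.

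SAP 7 lists one change for this endpoint, its move from safety to efficacy.

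**The concern.** A rate of this kind should divide the events by the women who could have had the event. Two features of the SAP rule depart from that.

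First, a woman with an ectopic pregnancy has a clinical pregnancy under the protocol's definition but cannot have an early abortion under it. She enlarges the denominator and can never enter the numerator.

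Second, denominator membership is settled at the Visit 5 scan, 4 to 6 weeks after transfer, while the numerator window opens at transfer. A β-hCG-positive woman who is given a miscarriage date before that scan, and has no positive clinical pregnancy result, would be in the numerator only. Both planned interval methods treat the count as a binomial count out of the denominator. If the numerator is not a subset of the denominator, that model does not apply.

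At stake are the reported rate in each arm and the interval for the difference between arms, for one secondary endpoint.

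**Working it through.** The documents state no early-abortion, ectopic or loss-to-follow-up rate, so there is no plan figure to reproduce. The check compares the texts and then sizes the effect on stated assumptions.

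**Inputs from the documents**
- 334 participants (Protocol 4.1), randomised 1:1 (Protocol 6.3.1): 334/2 = 167 per arm.
- Clinical pregnancy rate, for illustration: 40% (Protocol 2.2) to 61.8% (the Day 5 quality-control figure given as the reason for protocol version 2.0-CHN).
- Clinical pregnancies per arm: 167 × 0.40 ≈ 67; 167 × 0.618 ≈ 103.
- Visit 4 is Day 14 ± 1, Visit 5 is Day 35 ± 7 and Visit 6 is Day 63 ± 10 (Protocol 1.3).

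**Assumptions, not in the documents**
- Early-abortion rate r among intra-uterine clinical pregnancies: 10% to 15%.
- Ectopic share e of clinical pregnancies: 1% to 3%.

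**Ectopics in the denominator.** The SAP rate is r(1 − e), so the shortfall is r × e.
- Low: 0.10 × 0.01 = 0.10 points.
- High: 0.15 × 0.03 = 0.45 points.
- In counts: 8/67 = 11.9% becomes 8/65 = 12.3% once 2 ectopics are removed; 12/103 = 11.7% becomes 12/100 = 12.0% once 3 are removed.

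**Losses outside the denominator.** Each one adds 1 to the numerator and nothing to the denominator.
- n = 67: 9/67 − 8/67 = 1.5 points.
- n = 103: 13/103 − 12/103 = 1.0 point.
- The gap between Visit 4 and Visit 5 in which such a loss could fall runs from 28 − 15 = 13 days to 42 − 13 = 29 days.

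**Upper time limit.** The event definition stops at 12 completed weeks, and SAP 5 gives that timeframe, but the SAP 14.2 window runs to the end of the study. Visit 6 can fall on Day 73: 73/7 = 10.4 weeks after transfer, or about 12.4 weeks of pregnancy on the documents' two-week offset. The overrun is a few days at most, but the numerator text does not exclude it.

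**Scale.** The unstratified Miettinen-Nurminen 90% half-width for equal arms is 9.6 points (8/67 in each arm) or 7.6 points (12/103 in each arm). The ectopic shift is far inside this.

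**The case against.** The strongest reply is that the data flow probably keeps the numerator inside the denominator. Protocol Appendix 4 lists early miscarriage only among the Visit 6 data, and women who are negative at Visit 4 or Visit 5 go to end-of-study procedures. Protocol 7.2 treats a negative clinical pregnancy assessment as a separate ending from a heartbeat that stops later. A loss with no sac ever seen is also hard to classify as the loss of an intra-uterine pregnancy. This stands in part: there may be no such losses. It does not close the gap, because the SAP window opens at transfer, Appendix 4 provides for miscarriage at any point, and the early-miscarriage eCRF page is not shown.

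It is also fair to say that every spontaneous abortion and ectopic pregnancy is an SAE (Protocol Appendix 3), and that serious treatment-emergent events are tabulated and listed (SAP 15.1.1 and 15.2.2). On-treatment losses therefore stay visible whatever the rate formula.

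A reader might infer four stronger things that the documents do not support:

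- **That the SAP contradicts a protocol rate.** Protocol 9.4.3 gives no early-abortion rate.
- **That the rate would be badly inflated.** If 15% of β-hCG-positive women were lost before the scan and all were given a miscarriage date, 10/67 = 14.9% would become 22/67 = 32.8%. Neither condition is in the documents.
- **That the rule yields different answers in different hands.** Read literally, it names one eCRF page for each count and gives a single ratio. The problem is what that ratio means.
- **That the missing-data rule is an error.** Protocol 9.4.2 lets the SAP set endpoint-specific rules, and SAP 15.2.3 uses the same rule for bleeding. An example can be built in which the sign depends on the rule. With 12% risk among known outcomes and 5% v 10% unknown, the SAP rule gives 11.4% v 10.8%, and counting missing as an event gives 16.4% v 20.8%. Those missing rates are invented, and both differences (+0.6 and −4.4 points) lie inside the half-widths above.

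**Conclusion.** The point holds as a minor specification fault, with moderate confidence. That ectopics sit in the denominator follows directly from the protocol's two definitions and the SAP's rule, and no other section removes them. That the numerator is not restricted to women in the denominator is also plain from the text; whether it ever matters depends on an eCRF page that is not available.

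The ectopic effect is about 0.1 to 0.45 points, resting on the assumed abortion rate, the assumed ectopic share and roughly 67 to 103 clinical pregnancies per arm. The nesting effect is 1.0 to 1.5 points per affected woman, and possibly zero in total. There is no hypothesis test on this endpoint (Protocol 9.1; SAP 9), and the primary endpoint is untouched.

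**What to change.** In SAP 14.2, for early abortion:

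- Define the denominator as women with an intra-uterine clinical pregnancy.
- Define the numerator as early miscarriages before 12 completed weeks among those same women.
- List ectopic pregnancies, and losses before the Visit 5 scan, separately by arm.

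Optional: keep the current missing-data rule, show per arm how many clinical pregnancies have an unknown outcome, and add one sensitivity row that counts missing as an event. SAP 9 already presents missing observations as a separate category by default. The SAP 10.1 disposition percentages are based on all randomised women, so they do not give this count.

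The cost is a few lines of SAP text and a few table rows. No protocol change is needed and, on the protocol's own data lists, no new data: Visit 5 records ectopic pregnancy, and both event types are reported as SAEs. The reported rate may become slightly higher once ectopics leave the denominator.
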